5.1.2.4 Maintenance of ponesimod dose (Core and Extension Treatment Periods)

One tablet of study drug will be taken orally o.d., preferably in the morning, either before, with or after breakfast. It is preferable that the tablet be taken each day at approximately

Confidential

the same time. The tablet will be swallowed as a whole. During the Core Treatment Period only, the date and time of each study drug administration will be recorded by the subject in a diary.

On the day of the study visits, study drug must be administered only after the completion of the scheduled pre-dose safety assessments (systolic BP [SBP] and diastolic BP [DBP], ECGs, PFTs, laboratory tests) and PK sampling.

5.1.3 Blinding

Not applicable.

5.1.4 Study treatment supply

Manufacture, labeling, packaging and supply of study treatments will be conducted according to Good Manufacturing Practice, Good Clinical Practice (GCP) and any local or national regulatory requirements.

All treatment supplies are to be used only in accordance with this protocol and not for any other purpose.

5.1.4.1 Study treatment packaging and labeling

5.1.4.1.1 Study treatment packaging

Study treatment is provided as film-coated tablets and supplied in the following childproof bottles and childproof blister wallets:

- 6-day up-titration wallet containing two 2 mg tablets; two 3 mg tablets; two 4 mg tablets.
- 4-day up-titration wallet containing: one 6 mg tablet; one 7 mg tablet; one 8 mg tablet; one 9 mg tablet.
- 14 day up-titration wallet containing: two 2 mg tablets; two 3 mg tablets; two 4 mg tablets; one 5 mg tablet; one 6 mg tablet; one 7 mg tablet; one 8 mg tablet; one 9 mg tablet; three 10 mg tablets.
- 5 mg maintenance bottle containing thirty-six 5 mg tablets.
- 10 mg maintenance bottle containing thirty-six 10 mg tablets.
- 20 mg maintenance bottle containing thirty-six 20 mg tablets.

5.1.4.1.2 Study treatment labeling

Study treatment is labeled to comply with the applicable laws and regulations.

5.1.4.2 *Study treatment distribution and storage*

Treatment supplies must be kept in an appropriate, secure area and stored according to the conditions specified on the medication labels. Ponesimod must not be stored above 25 °C (recommended storage is 15–25 °C).

5.1.4.3 *Study treatment dispensing*

The subjects will receive sufficient study treatment to cover the period up to the next scheduled visit. Subjects are asked to return all used, partially used and unused study treatment blister wallets and/or bottles at each protocol-scheduled visit. An accurate record of the date and amount of study treatment dispensed to each subject must be available for inspection at any time.

5.1.4.4 *Study treatment return and destruction*

On an ongoing basis and/or on termination of the study, the monitor will collect used and unused bottles or blister wallets, which will be sent to the warehouse, where Actelion or a deputy will check treatment reconciliation.

5.1.5 Drug accountability and compliance

5.1.5.1 *Drug accountability*

Records of study drug dispensed and returned, dosages administered, and intervals between visits are kept during the study. Study treatment accountability must be performed by the study staff on the day of the visit and before providing further study treatment, in order to ensure that the subject is compliant with study requirements. Study treatment accountability is checked by the monitor during site visits and at the end of the study.

5.1.5.2 *Drug compliance*

Core Treatment Period

Subjects' compliance with study drug intake will be monitored using a diary. On each day, the subjects will be asked to enter the date, time, number of tablets taken, and the unique bottle or blister wallet identifying number from which the tablets were taken from. In addition, during the up-titration, the position of the well on the blister wallet will be recorded in order to monitor that study drug tablets were taken in the correct sequence [see Section 5.1.2.1].

The study drug accountability performed by the site at each visit [see Section 5.1.5.1] will be used to crosscheck the subject's compliance as indicated in the diary. Identified discrepancies will be reconciled by the site. Subjects will be asked to explain the observed discrepancies. Interruptions with known dates will be recorded accordingly in the study drug log [see Section 5.1.6]. Study drug intake requirement will be re-explained to the subject each time an interruption is observed.

Confidential

Extension Treatment Period

The study drug accountability performed by the site at each visit [see Section 5.1.5.1] will allow to assess the subject compliance. Interruptions with known dates will be recorded accordingly in the study drug log [see Section 5.1.6]. Study drug intake requirements will be re-explained to the subject each time an interruption is observed.

5.1.6 Ponesimod dose adjustments and interruptions

Ponesimod up-titration, other than described in Section 5.1.2, is prohibited. Ponesimod dose reduction is permitted under some circumstances [see Section 5.1.10].

Ponesimod interruption should be avoided. If ponesimod intake is interrupted by the subject for any reason, he/she must immediately inform the investigator.

Ponesimod may be temporarily interrupted in response to an AE, a diagnostic or therapeutic procedure, a laboratory abnormality, or for administrative reasons. Study-specific criteria for interruption of ponesimod are described in Section 5.1.10.

Detailed guidance on how to re-initiate ponesimod in the event of drug interruption is provided in Section 5.1.8.

Ponesimod dose adjustments / interruptions must be recorded in the eCRF.

5.1.7 Cardiac monitoring for ponesimod initiation and re-initiation requiring re-up titration

Subjects must undergo cardiac monitoring at the site on Day 1 (Visit 2 - ponesimod initiation) and EX-1 (Visit 11 - ponesimod treatment initiation in the extension).

Subjects must also undergo cardiac monitoring at the site on the first day of any ponesimod re-initiation requiring up-titration.

Cardiac monitoring is overseen by the cardiac safety assessor and consists of the following:

- Pre-dose: 12-lead ECG; systolic/diastolic BP measurement.
- Hourly post-dose, starting 1 hour post-dose: 12-lead ECG; systolic/diastolic BP measurement. ECG and BP are recorded hourly until the subject is discharged from monitoring.
- Discharge from monitoring at least 4 hours post-dose, as per “Discharge from Cardiac Monitoring Criteria” below.

Discharge from Cardiac Monitoring Criteria

After the collection of the 12-lead ECG and systolic/diastolic BP measurement at 4 hours post-dose and up to 12 hours post-dose, the subject may be discharged from the clinic and continue on ponesimod as soon as all of the following are met:

- ECG-derived resting HR > 45 bpm on the last ECG. If ECG-derived resting HR < 50 bpm on the last ECG, then HR at last ECG must be higher than at least one HR recorded on any prior post-dose ECG.
- SBP > 90 mmHg.
- QTcF < 481 ms on the last ECG.
- Increase in QTcF on the last ECG versus pre-dose ECG must be < 60 ms.
- No persisting significant ECG abnormality (e.g., QT prolongation, AV block second degree or higher) or ongoing AE requiring continued hospitalization or prohibiting study continuation as an outpatient.

Should the subject not meet the criteria for discharge at 12 hours post-dose, he/she must be discontinued from ponesimod. Subjects who are discontinued may be discharged from the monitored setting only after the following criteria are met:

- Vital signs return to near baseline values.
- No persisting ECG abnormality (e.g., AV block second degree or higher).
- No ongoing AE requiring continued hospitalization.
- Absence of any other medical indication to remain in the monitoring setting.

5.1.8 Procedures for re-initiation of ponesimod in the event of interruption

Under no circumstances should a subject take more than one tablet per day.

Terminology

- Interruption: a day or the days where subject did not take a prescribed ponesimod dose.
- Re-initiation: the day a ponesimod dose is taken following an interruption.
- Re-initiation with up-titration: Re-initiation of a gradually increasing ponesimod dose regimen that reaches a target dose over several days. Not all re-initiations include up-titration.

If ponesimod intake is interrupted by the subject for any reason, the subject must immediately inform the investigator. The investigator and subject must adhere to the mandatory procedures described here regarding re-initiation.

Confidential

Mandatory procedures for the following five interruption scenarios:

Scenario 1: Subject missed taking 1 to 3 consecutive doses, with first dose missed on study Day 2–6. (Scenario 1 applies to Core Treatment Period only.)

- Ponesimod must be re-initiated within 3 days of last missed dose, otherwise ponesimod is prematurely discontinued.
- The following up-titration scheme using a titration blister wallet needs to be applied:

6 day up-titration scheme		
Re-initiation Day	Ponesimod Daily Dose	Given at site with monitoring
1	2 mg	Yes
2	2 mg	No
3 and 4	3 mg	No
5 and 6	4 mg	No
7, 8, ...	5 mg	No

- Re-initiation with up-titration for scenario 1 is allowed only once during the study, otherwise ponesimod is prematurely discontinued.

Scenario 2: Subject missed taking \geq 4 consecutive doses, with first dose missed during study Days 2–56. (Scenario 2 applies to Core Treatment Period only.)

- Subjects may only be re-initiated on ponesimod as per protocol and per investigator judgment, and according to the up-titration schemes in Scenario 4 below. Subsequent dose escalation from 5 mg to 10 mg or from 10 mg to 20 mg, whichever is relevant, is prohibited.

Scenario 3: Subject missed taking 1 to 3 consecutive doses any time after study Day 6. (Scenario 3 applies to both Core and Extension Treatment Periods.)

- Dosing should be re-initiated at the same dose as the dose taken prior to ponesimod interruption, **with the following exceptions (exceptions apply to the Core Treatment Period only):**
 - i. If the interruption occurs during Core Treatment Period Days 29–32 (up-titration to 10 mg), the missed dose(s) is/are taken to complete remaining doses in the titration blister wallet
 - ii. If the interruption includes Core Treatment Period Day 57 (dose-escalation to 20 mg), the 10 mg dose is restarted, and a clinic visit is scheduled to conduct required assessments (e.g., ECG) prior to dose escalation to 20 mg
- Ponesimod intake may be re-initiated by the subject at home.
- Subjects must be instructed to contact the investigator immediately if they experience any symptoms of bradycardia (e.g., dizziness, vertigo, syncope).

Scenario 4: Subject missed taking ≥ 4 consecutive doses during study Days 57–148 (Core Treatment Period) or at any time during the Extension Treatment Period.

- The following up-titration scheme using a titration blister wallet is applied if the ponesimod 5 mg dose is targeted. Ponesimod must be re-initiated within 10 days of last missed dose, otherwise ponesimod is prematurely discontinued (discontinuation applies to Core Treatment Period only).

6 day up-titration scheme		
Re-initiation Day	Ponesimod Daily Dose	Given at site with monitoring
1	2 mg	Yes
2	2 mg	No
3 and 4	3 mg	No
5 and 6	4 mg	No
7 to EOT1, 2	5 mg	No

- The following up-titration scheme using a titration blister wallet is applied if the ponesimod 10 mg dose is targeted. Ponesimod must be re-initiated within 10 days of last missed dose, otherwise ponesimod is prematurely discontinued (discontinuation applies to Core Treatment Period only).

14 day up-titration scheme		
Re-initiation Day	Ponesimod Daily Dose	Given at site with monitoring
1	2 mg	Yes
2	2 mg	No
3 and 4	3 mg	No
5 and 6	4 mg	No
7	5 mg	No
8	6 mg	No
9	7 mg	No
10	8 mg	No
11	9 mg	No
12, 13, and 14	10 mg	No
Day 15 to EOT1, 2	10 mg	No

- The following up-titration scheme using a titration blister wallet is applied if the ponesimod 20 mg dose is targeted. Ponesimod must be re-initiated within 10 days of last missed dose, otherwise ponesimod is prematurely discontinued (discontinuation applies to Core Treatment Period only).

14 day up-titration scheme		
Re-initiation Day	Ponesimod Daily Dose	Given at site with monitoring
1	2 mg	Yes
2	2 mg	No
3 and 4	3 mg	No
5 and 6	4 mg	No
7	5 mg	No
8	6 mg	No
9	7 mg	No
10	8 mg	No
11	9 mg	No
12, 13, and 14	10 mg	No
Day 15 to EOT1, 2	20 mg	No

- Re-initiation with up-titration for scenario 4 is allowed only once during the Core Treatment Period, otherwise ponesimod is prematurely discontinued.
- Re-initiation with up-titration for scenario 4 may be permitted more than once during the Extension Treatment Period if it is in the best interest of the subject. The investigator should discuss with Actelion.

Scenario 5:

Subject missed taking \geq 4 consecutive doses during study Days 149–167.

- Ponesimod is prematurely discontinued and an EOT1 visit is conducted.

Confidential

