5.1.2.2 Titration

Core Treatment Period

A 6-day up-titration will occur during study Days 1–6 using a titration blister wallet, to reduce ponesimod first-dose effects. On-site subject monitoring will be required at enrollment on Day 1 [see Section 5.1.7]. A 4-day up-titration will occur during study Days 29–32 to gradually transition from the 5 mg to the 10 mg daily dose. The subject will have the dose escalated from 10 to 20 mg on Day 57 (without gradual up-titration). The first day of the 4-day up-titration (Day 29) and the Day 57 dose escalation do not require on-site monitoring. [See Table 3].

Table 3 Up-titration and dose-escalation schedule: Core Treatment Period

Treatment Course		Study Day	Ponesimod Daily Dose
1	6-day up-titration	1 (Enrollment)	2 mg (first dose given on-site with monitoring)
		2	2 mg
		3 and 4	3 mg
		5 and 6	4 mg
	5 mg daily	7 to 28	5 mg
2	4-day up-titration	29 (Week 4)	6 mg
		30	7 mg
		31	8 mg
		32	9 mg
	10 mg daily	33 to 56	10 mg
3	Dose escalation to 20 mg	57 (Week 8)	20 mg
	20 mg daily	58 to day before EOT1 (Week 24)	20 mg

EOT1 = End-of-Treatment for the Core Treatment Period

Extension Treatment Period

A 6- or 14-day up-titration will occur starting at Visit EX-1 using a titration blister wallet, to reduce ponesimod first-dose effects. On-site subject monitoring will be required at enrollment at Visit EX-1 [see Section 5.1.7]. The choice of the 6- or 14-day up-titration will depend on the targeted dose: 5 mg, 10 mg, or 20 mg. The targeted dose is the subject's previously tolerated ponesimod dose just prior to EOT1. [See Table 4].

Table 4 Up-titration schedule: Extension Treatment Period

- The following up-titration scheme using a titration blister wallet is applied if the ponesimod 5 mg dose is targeted.

6 day up-titration scheme		
Day(s)	Ponesimod Daily Dose	Given at site with monitoring
1 (Visit EX-1)	2 mg	Yes
2	2 mg	No
3 and 4	3 mg	No
5 and 6	4 mg	No
7 to EOT2	5 mg	No

- The following up-titration scheme using a titration blister wallet is applied if the ponesimod 10 mg dose is targeted.

14 day up-titration scheme		
Day(s)	Ponesimod Daily Dose	Given at site with monitoring
1 (Visit EX-1)	2 mg	Yes
2	2 mg	No
3 and 4	3 mg	No
5 and 6	4 mg	No
7	5 mg	No
8	6 mg	No
9	7 mg	No
10	8 mg	No
11	9 mg	No
12, 13, and 14	10 mg	No
15 to EOT2	10 mg	No

- The following up-titration scheme using a titration blister wallet is applied if the ponesimod 20 mg dose is targeted.

14 day up-titration scheme		

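### Restart rules keyed to study day send a 1–3 dose gap during Extension up-titration or later Core re-titration to an at-home, same-dose restart, which conflicts with other sections and often cannot be met from the wallet

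*Combined protocol and SAP*

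**What the plan says.** Section 5.1.8 of the protocol sets mandatory procedures for five interruption scenarios. Two of them deal with gaps of one to three doses.

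- **Scenario 1** is worded as follows: "Subject missed taking 1 to 3 consecutive doses, with first dose missed on study Day 2–6. (Scenario 1 applies to Core Treatment Period only". The subject restarts at 2 mg on site with monitoring. This is permitted once; otherwise the drug is stopped.
- **Scenario 3** is worded as follows: "Subject missed taking 1 to 3 consecutive doses any time after study Day 6. (Scenario 3 applies to both Core and Extension Treatment Periods". The instruction is "Dosing should be re-initiated at the same dose as the dose taken prior to ponesimod interruption", and "Ponesimod intake may be re-initiated by the subject at home". There are two exceptions, for Days 29–32 and for a gap that includes Day 57, and these "exceptions apply to the Core Treatment Period only".

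Scenarios 2, 4 and 5 all need at least four missed doses.

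For the Extension, Section 5.1.2.2 states: "A 6- or 14-day up-titration will occur starting at Visit EX-1 using a titration blister wallet, to reduce ponesimod first-dose effects". Table 4 gives Extension Days 1–6 the same steps as Core Days 1–6 in Table 3: 2, 2, 3, 3, 4, 4 mg. The first dose is monitored in both. Section 5.1.4.1.1 lists what each titration wallet holds.

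**The concern.** The scenarios are tied to study day and not to the position in the titration being followed. Section 8 and the Table 1 notes count days from Visit 2, so every Extension day comes after study Day 6. One gap in one sequence of steps thus has two different restart procedures, depending only on the period or calendar day.

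The rule concerns cardiac safety: Section 1.3.2.4 names heart rate and AV conduction changes as the most prominent safety signal. Sites need a single rule that they can carry out. Section 5.1.6 forbids any up-titration other than the one described, so a site whose wallet lacks the required tablet has no described step to follow. Data are affected too. Section 6.2.3 includes ECG change on the day of re-initiation as a safety endpoint, so whether those ECGs exist depends on which passage the site follows.

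**Working it through.** **1. Which scenario applies to a 1–3 dose gap**

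| When the gap falls | Scenario | Restart |
|---|---|---|
| Core Days 2–6 (first miss) | 1 | 2 mg, on site, monitored, once only |
| Extension Days 2–14 of up-titration | 3 | last-taken dose, home allowed |
| Core re-titration, after study Day 6 | 3 | last-taken dose, home allowed |
| Core Days 29–32, or gap including Day 57 | 3, exception (i) or (ii) | as the exception states |

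If study Day 6 is instead read as Extension Day 6, a gap on Extension Days 2–6 falls under no scenario, because Scenario 1 is limited to the Core. Extension Days 7–14 would still be Scenario 3.

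**2. Core re-titration, worked example.** A subject misses Day 2 and restarts on Day 3. Re-initiation Day 4 is study Day 6. A second miss there is Scenario 1 again, and the once-only limit stops the drug. A miss one day later, on study Day 7, is Scenario 3 and allows a home restart.

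**3. Other sections**

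- Section 5.1.8 defines re-initiation as the day on which a dose is taken after an interruption. Section 7.3.1 requires a pre-dose ECG and then hourly ECGs for at least 4 hours on the day of re-initiation. A Scenario 3 restart at home cannot satisfy that.
- Section 5.1.7 requires monitoring on the first day of any re-initiation that needs up-titration. Resuming a part-finished titration can be read as one.
- Appendix 3(a), for an interruption made during up-titration, assumes that an up-titration follows the restart.

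**4. Wallet count.** Inputs are Section 5.1.4.1.1 and Table 4. The 14-day wallet holds 2+2+2+1+1+1+1+1+3 = 14 tablets and the 6-day wallet 2+2+2 = 6. Both match the schedule exactly, with no spares. For each first-missed day, the check is whether a tablet of the last-taken strength is left.

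| First missed day (14-day wallet) | Last dose (mg) | Tablets left of that strength |
|---|---|---|
| 2 | 2 | 1 |
| 3 | 2 | 0 |
| 4 | 3 | 1 |
| 5 | 3 | 0 |
| 6 | 4 | 1 |
| 7 | 4 | 0 |
| 8, 9, 10, 11, 12 | 5, 6, 7, 8, 9 | 0 each |
| 13 | 10 | 2 |
| 14 | 10 | 1 |

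None is left for Days 3, 5 and 7–12, which is 8 of 13. With a 20 mg target, a first miss on Day 15 also fails (last dose 10 mg, none left), giving 9 of 14.

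With the 6-day wallet, Days 3 and 5 fail, 2 of 5. A first miss on Day 7 (last dose 4 mg, none left) makes it 3 of 6. That Day 7 case also arises in the initial Core titration.

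**5. How close the Extension restart is to a first exposure (indicative).** Section 1.3.2.1 gives a half-life of about 32 h. Assuming simple exponential decline, the fraction remaining is 2^(−hours/32).

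- 7 days off drug (168 h): 2^(−5.25) = 2.6%
- No missed dose (24 h): 59%
- One, two or three missed doses (48, 72, 96 h): 35%, 21%, 12.5%

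**The case against.** The best defence is that much of the protection remains. The dose at EX-1 and the first day of each re-titration are monitored. A gap of four or more doses in the Extension requires a monitored 2 mg restart. Scenario 3 repeats a dose already taken, any interruption must be reported to the investigator at once, and subjects must report bradycardia symptoms. All of this stands. A reader might infer that first-dose cardiac protection is lost; the documents do not support that. What differs is the handling of a 1–3 dose gap.

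Three further inferences also fail.

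- *Every second miss in a Scenario 1 re-titration escapes the once-only limit.* With restart on the day after the last missed dose, re-initiation Day 2 is study day (first-missed day + gap length + 1). That is Day 6 or earlier in 6 of the 15 combinations of first-missed day (2–6) and gap length (1–3), so the limit still applies there.
- *Scenario 3 can never be followed during titration.* The count shows positions where it can, and Section 8.5.2 allows new blisters to be dispensed at an unscheduled visit. A missing strength means a resupply step.
- *Every Extension or re-titrated subject is affected.* Only those who miss 1–3 doses while titrating are, in a trial of about 30 subjects where only completers who progress may enter the Extension.

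The defence can add that neighbouring sentences in Section 7.3.1 limit monitoring to restarts where it is required, and that Section 5.1.8 says not all re-initiations include up-titration. Appendix 3 matters here only if the interruption lasts 1–3 doses. These points make the conflicts with Section 5.1.7 and Appendix 3 a matter of reading. They leave the unqualified ECG sentence in Section 7.3.1 at odds with a home restart, and they do not explain the different handling of identical steps.

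**Conclusion.** The restart rules are wrong as written and should be amended. A mandatory procedure on cardiac safety handles the same 1–3 dose gap in the same steps differently by period and calendar day, without a stated reason. It conflicts with Section 7.3.1 and can be read as conflicting with Section 5.1.7 and Appendix 3. Its same-dose instruction cannot be met from the wallet for 8 of 13 first-missed days (14-day wallet) or 2 of 5 (6-day wallet), plus a first miss on Day 7 of the 6-day schedule.

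The scenario assignment rests on study day being counted from Visit 2; the alternative reading leaves part of the Extension under no scenario. The wallet counts assume no resupply. The documents give no heart-rate or AV data after 1–3 doses missed during titration, so the clinical risk cannot be sized and the residual-drug figures are only indicative. Nothing here shows which restart rule is right.

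**What to change.** Reconcile Section 5.1.7, Section 5.1.8 (Scenarios 1 and 3), Section 7.3.1, Section 8.5.1, Appendix 3 and the wallet contents in Section 5.1.4.1.1.

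- Define the scenarios by day of the current up-titration (initial, Extension or re-initiation) instead of by study day.
- For each, state whether on-site monitoring applies.
- For each, state which tablets are used and where they come from when the wallet no longer holds the required strength.
- Carry the same wording into every section listed.

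The choice of clinical rule belongs to the sponsor's medical team. The cost is a protocol amendment and, depending on that choice, possibly a few extra monitored visits or replacement wallets.

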5.1.10.3 Hepatobiliary

In case of abnormal liver tests or signs and symptoms suggestive of drug-induced liver injury, subjects will be closely observed, liver tests will be repeated, and ponesimod may need to be prematurely discontinued or interrupted.

The central laboratory will send alerts to the principal investigator and the sponsor whenever any of the following hepatobiliary laboratory abnormalities are recorded during the study:

- \geq Grade 2 elevation ALT ($> 3 \times \text{ULN}$)
- \geq Grade 2 elevation AST ($> 3 \times \text{ULN}$)
- \geq Grade 2 elevation blood bilirubin (same as TBL) ($> 1.5 \times \text{ULN}$)

The site will immediately contact the subject and ask him/her to return to the site within 72 hours, at the latest, to repeat the test by the central laboratory (unless the clinical situation mandates immediate local testing). An inquiry should be made about symptoms.

Should repeat testing confirm continuing abnormality, the following will apply:

Ponesimod must be prematurely discontinued for any of the following:

- Grade 4 ALT or AST elevation ($> 20.0 \times \text{ULN}$).
- Grade 4 blood bilirubin (same as TBL) elevation ($> 10.0 \times \text{ULN}$).
- Grade 2 or higher ALT or AST elevation ($> 3 \times \text{ULN}$) and (TBL $> 2 \times \text{ULN}$ or international normalized ratio [INR] > 1.5 ; corresponds to Hy's Law).
- Grade 2 or higher ALT or AST elevation ($> 3 \times \text{ULN}$) with the appearance of: fatigue, nausea, vomiting, right upper quadrant pain or tenderness, fever, rash, and/or eosinophilia ($> 5\%$).
- Grade 3 or higher ALT or AST elevation ($> 5.0 \times \text{ULN}$) during study Days 2–56 or study Days 149–168.
- Grade 3 or higher TBL elevation ($> 3.0 \times \text{ULN}$) during study Days 2–56 or study Days 149–168.
- Grade 3 or higher ALT or AST elevation ($> 5.0 \times \text{ULN}$) and subject is taking ponesimod 5 mg.
- Grade 3 or higher TBL elevation ($> 3.0 \times \text{ULN}$) and subject is taking ponesimod 5 mg.

Please see box “Monitoring for all subjects with confirmed \geq grade 2 AST, ALT, or TBL elevations”.

Confidential

Ponesimod is interrupted for any of the following:

- Grade 3 ALT or AST elevation ($> 5.0\text{--}20.0 \times \text{ULN}$) during study Days 57–148 or during the Extension Treatment Period.
- Grade 3 TBL elevation ($> 3.0\text{--}10.0 \times \text{ULN}$) during study Days 57–148 or during the Extension Treatment Period.

Procedure for interruption

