- Interrupt ponesimod for at least 7 days.
- Perform a re-test of AST, ALT, TBL within 7 days.
- If elevated values do not return to baseline levels within 7 days following treatment interruption, **ponesimod is prematurely discontinued. Please see box “Monitoring for all subjects with confirmed \geq grade 2 AST, ALT, or TBL elevations”.**
- If elevated values return to baseline levels within 7 days following treatment interruption, **ponesimod is re-initiated with up-titration.**

Procedure for re-initiation with up-titration

- Re-initiation occurs 8–10 days after ponesimod was interrupted.
- The previously tolerated dose is targeted at re-initiation with up-titration. For subjects on ponesimod 10 mg at the time of interruption, the 5 mg dose is targeted. For subjects on 20 mg at the time of interruption, the 10 mg dose is targeted. Subjects remain on the lower dose for the remainder of the study, with no further dose-escalation.
- **Re-initiation and up-titration should be conducted in accordance with Section 5.1.8, scenario 4.**

Perform a re-test of AST, ALT, TBL at 5–7 and 10–12 days following re-initiation, and monthly thereafter. Recurrence of \geq grade 3 AST, ALT, TBL results in premature discontinuation with follow-up monitoring.

Please see box “Monitoring for all subjects with confirmed \geq grade 2 AST, ALT, or TBL elevations”.

Confidential

Monitoring for all subjects with confirmed \geq grade 2 AST, ALT, or TBL elevations

- Monitoring continues even after ponesimod discontinuation or interruption.
- AST, ALT, and TBL are re-tested weekly, and more frequently if indicated, until laboratory abnormalities are no longer regarded as clinically relevant.
- Follow-up monitoring, including more frequent visits, is provided until signs and symptoms have resolved or until medically indicated.
- Further diagnostic work-up/consultation with a hepatologist or other specialist should be considered according to local practice and the clinical situation.

Any clinically relevant finding found after ponesimod initiation and during the follow-up period and meeting the definition of an AE will be recorded in the eCRF.

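### For a liver-test interruption that crosses Day 148/149, Sections 5.1.8 and 5.1.10.3 can require both restart and discontinuation; other crossing runs of missed doses fit both scenarios or neither

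*Combined protocol and SAP*

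**What the plan says.** **Section 5.1.10.3 (Hepatobiliary).** A confirmed Grade 3 ALT, AST or total bilirubin rise leads to interruption if it occurs "during study Days 57–148 or during the Extension Treatment Period". The same rise leads to discontinuation if it occurs "during study Days 2–56 or study Days 149–168", or if the subject is on 5 mg. After an interruption, ponesimod is restarted only if values return to baseline within 7 days. The timing is fixed: "Re-initiation occurs 8–10 days after ponesimod was interrupted". So is the procedure: "Re-initiation and up-titration should be conducted in accordance with Section 5.1.8, scenario 4".

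**Section 5.1.8 (re-initiation scenarios, described there as mandatory).**
- Scenario 2 covers four or more missed doses and is keyed to where the run begins: "with first dose missed during study Days 2–56".
- Scenario 3 covers only one to three missed doses.
- Scenario 4 covers four or more "consecutive doses during study Days 57–148 (Core Treatment Period) or at any time during the Extension Treatment Period". It allows restart with up-titration, once only in the Core period.
- Scenario 5 covers four or more consecutive missed doses during Days 149–167. Its whole instruction is: "Ponesimod is prematurely discontinued and an EOT1 visit is conducted".

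Section 5.1.6 lists laboratory abnormalities among the reasons for interruption and refers to Section 5.1.8 for re-initiation, so liver interruptions come under these scenarios.

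**The concern.** A restart 8–10 days after an interruption late in the Scenario 4 window falls well inside the Scenario 5 window. Section 5.1.10.3 then says restart, Scenario 5 says stop, and no text ranks them.

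The two routes lead to different places:
- **Restart:** treatment to Week 24, the Week 24 assessment, 90 days of follow-up (Section 3.2.3) and possible Extension entry (Section 4.6).
- **Scenario 5:** EOT1 at once, 30 days of follow-up (Section 3.2.3), no chronic GVHD activity assessment at FU1 (Table 1, note 9), no Extension entry because 24 weeks were not completed (Section 4.6), and probable loss from the Per-protocol set (Section 11.1.3).

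If sites follow different pages, the count of premature discontinuations, the Week 24 response data and Extension entry depend partly on that choice. In a study of 30 subjects, each reclassified subject is visible in the tables.

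**Working it through.** **1. Day numbering.** Table 3 gives Week 4 = Day 29 and Week 8 = Day 57. The rule Day = 7 × week + 1 reproduces both (7×4+1 = 29; 7×8+1 = 57). It gives Week 20 = Day 141 and Week 24 = Day 169.

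**2. Counting rule.** Let s be the first missed day (s ≤ 148) and L the number of consecutive missed doses, so the restart day is s + L. For a run crossing Day 148/149 and ending by Day 167:
- missed doses in Days 57–148: 149 − s, which is at least 4 when s ≤ 145 (Scenario 4 met);
- missed doses in Days 149–167: s + L − 149, which is at least 4 when s + L ≥ 153 (Scenario 5 met).

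**3. Liver interruptions.** If the interruption day is the first missed dose, a restart 8–10 days later means L = 8, 9 or 10.

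| Missed doses L | Start days s (up to 148) that meet Scenario 5 |
|---|---|
| 8 | 145–148 |
| 9 | 144–148 |
| 10 | 143–148 |

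Examples:
- s = 145, L = 8: restart Day 153, split 4 and 4, so both scenarios are met.
- s = 148, L = 8: restart Day 156, split 1 and 7. The missed doses meet only Scenario 5, yet Section 5.1.10.3 names Scenario 4.
- s = 144, L = 8: restart Day 152, split 5 and 3, so there is no conflict.

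Starts on Days 145–148 conflict for every permitted restart. Day 144 conflicts with 9 or 10 missed doses, and Day 143 only with 10.

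**4. Other way of counting.** If the 8–10 days run from the last dose taken, L is 7, 8 or 9. With L = 7, Scenario 5 needs s ≥ 146. A first missed dose on Days 146–148 then always conflicts, Day 145 only with 8 or 9 missed doses, and Day 144 only with 9. The limits move by about one day.

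**5. Missed doses in general.**
- *Neither scenario* (s ≥ 146 and s + L ≤ 152): Days 146–149, 147–150, 148–151, 146–150, 147–151 and 146–151. Scenario 3 stops at three doses, so these runs of 4–6 have no procedure.
- *Both scenarios* (s ≤ 145 and s + L ≥ 153): possible from 8 missed doses, for example Days 145–152 (4 and 4), 144–152 (5 and 4) and 143–152 (6 and 4).
- If the whole run had to lie inside one window, every crossing run of four or more would fit neither.

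**6. Link to a scheduled visit.** The Week 20 visit is nominally Day 141 with a window of ±7 days (Days 134–148). The repeat test is due within 72 hours of contact, so a nominal-day sample could be confirmed by about Day 144 plus laboratory turnaround, which is not given. Across the window the same sum runs from about Day 134 to Day 151 or later. A Week 20 result can therefore lead to an interruption in the conflict span, but need not.

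**The case against.** The best defence is that Scenarios 1 and 2 are classified by the first missed dose, and that the liver windows almost mirror Scenarios 4 and 5. Reading all the scenarios by first missed dose removes both the overlap and the gap. Section 5.1.10.3 also names Scenario 4 specifically, and a specific rule might be taken to override a general one. This reading is coherent, but Scenarios 4 and 5 are not worded that way and no precedence is stated. A site that follows Scenario 5 literally is not in error.

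The case is also narrow, and that stands. Restart requires all of the following: a confirmed Grade 3 rise, a dose above 5 mg, no discontinuation criterion met, return to baseline within 7 days, and Scenario 4 not already used in the Core period. Otherwise ponesimod is discontinued and there is no conflict. The documents give no rate for such events, and it is conjecture that sites would in fact diverge.

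Three stronger readings are tempting but not supported:
- *Every confirmed Grade 3 result at Week 20 runs into the conflict.* The visit window and the unstated laboratory turnaround rule this out.
- *A subject still re-titrating at EOT1 would carry a titration step into the Extension, because the target is the "previously tolerated ponesimod dose just prior to EOT1".* Sections 5.1 and 5.1.2.2 limit the Extension dose to 5, 10 or 20 mg, and Section 5.1.10.3 keeps the liver subject on the lower target dose for the rest of the study.
- *The primary result is at risk.* The primary variable ends at Week 12. Week 24 response is exploratory and summarised descriptively.

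**Conclusion.** The concern holds as a conflict between two mandatory rules over a short span. For a subject who meets all the restart conditions, interruptions starting on about Days 145–148 fall under both instructions, as do those on Days 143–144 with later restarts. The exact limits depend on whether the interruption day is the first missed dose or the last dose taken. Separately, six crossing runs of 4–6 missed doses have no assigned procedure, and some runs of 8 or more have two. These counts assume that a dose belongs to a scenario's window if it was missed on a day inside it. Few subjects are likely to be affected. For any who are, the choice settles discontinuation status, length of follow-up, the Week 24 assessment and Extension eligibility. The passages should be reconciled.

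**What to change.** Reconcile Section 5.1.8 (Scenarios 2, 4 and 5) with the interruption and re-initiation procedures in Section 5.1.10.3:
1. Use one anchor for Scenarios 2, 4 and 5, so that each run of four or more missed doses maps to exactly one scenario, including runs that cross Day 148/149.
2. State which section takes precedence when a protocol-mandated liver interruption begun by Day 148 runs past Day 149.
3. State whether the 8–10 days run from the last dose taken or from the first dose missed.

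Which clinical outcome applies is for the sponsor to decide. The cost is a few sentences in two sections, with no new procedures.
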